7. BACKGROUND AND SIGNIFICANCE

Clinical:

Approximately 517,000 infants are born prematurely every year¹, and as low birth weight and premature infants are surviving longer, they are at high risk of developing severe ROP. In the United States, 2,000 infants per year are diagnosed with severe ROP, which is the leading cause of irreversible childhood blindness in the United States. In our NICU, we care for between 60 and 80 infants each year that are born with low birth weight.

Usual parenteral nutrition protocols do not meet the infants' fetal accretion rates. Despite receiving 14-28 mg DHA/kg/day,² preterm infants have lower serum DHA and EPA levels than they would have had *in utero*, and

their tissues have lower n-3 and n-6 fatty acid than full term infants, indicating that their dietary needs are often not met.³ Preterm and small for gestational age infants have altered serum phospholipid fatty acid profiles with lower DHA and polyunsaturated omega-3 fatty acids than appropriate for gestational age infants.⁴ Low birth weight infants often have severe lung disease and are exposed to exogenous oxygen, which causes retinal blood vessel attenuation, retinal hypoxia, up regulation of pro-angiogenic factors, and neovascularization, which can lead to irreversible vision loss.

In a recent Polish prospective interventional study, Pawlik et al. showed that in preterm infants (average 28 week gestation, 935 gram birth weight), continuous intravenous n-3 fatty acids with Omegaven® from day one to day 28 of life, followed by enteral omega-3 fatty acids is safe and resulted in a significantly decreased need for ROP laser treatment. In the treatment group, 9 of 60 infants needed laser compared with 22 of 70 infants in the control group.^{7,12} On treatment, infants had higher plasma and red blood cell DHA levels at 7 and 14 days and a lower risk for cholestasis. This study showed that treatment was well tolerated in preterm infants and that Omegaven® has a positive effect on ROP pathogenesis, but no investigations were done into the mechanisms by which ROP was suppressed in the experimental group compared with the control arm. There is also no clinical data that currently differentiates the differences in the blood biology (fatty acids, gene expression, and proteins) in infants with and without severe ROP.

Translational:

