9. RESEARCH DESIGN AND METHODS

The treatment duration for the study will begin 0-7 days of life and continue until 40 weeks adjusted age (full-term). Intravenous treatment will start in the first few days of life and will continue until the infant can tolerate enteral nutrition. Once enteral feeds can be started, supplementation by mouth will begin until 40 weeks adjusted age.

Laboratory blood draws:

Prior to enrollment: In addition to routine tests, blood will be tested for AST and ALT. If these tests are interpreted as abnormal, the infant will not be considered for enrollment in the study as it will be deemed a contraindication to supplemental Omegaven.

While the infant is growing in the hospital, the doctors will need to check the infant's blood to make sure the infant is developing as expected.

If the infant is enrolled in the study, the infant will be randomized in blocks of 4 by gestational age to one of two groups. The control group will get standard of care nutrition, and the experimental group will get standard of care nutrition with supplemental omega-3 fatty acids. Soon after birth, most premature infants need additional nutrition through the vein (intravenous). For the control group, there will be no changes to the standard of care parenteral nutrition. For the experimental group, the infant will receive Omegaven, an intravenous lipid preparation prepared from highly refined fish oil, in addition to the standard of care parenteral nutrition. In the instance that twins are enrolled in the study, the siblings will be randomized as one to receive the same treatment per request and approval from [name].

Transition – For the second/interventional group, Omegaven will be stopped once enteral feeds are at 120 ml/kg and enteral Oil will be started. There will be no overlap of parenteral and enteral n-3 supplementation.

If the infant can start using his/her own stomach for digestion, he/she will get fatty acid supplementation. In the control group, the infant will receive standard of care feeding. If the infant is in the experimental group, the infant will get one fourth (1/4) teaspoon per kilogram per day ($1.25\text{mL/kg/day} = 400\text{ mg omega3 per kg of fish oil per day}$) of Carlson's fish oil oral solution. Dose will be divided to at least twice a day dosing for better tolerance.

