We will examine the infant's eyes according to the standard NICU guidelines and protocols. We will also examine the infant's eyes in our eye clinic after discharge over time as we do for all premature infants to support the infant's visual development.

During the study:

Maternal diet questionnaires will be administered to the maternal subjects following enrollment. This questionnaire is the Omega 3 Fatty Acid Questionnaire and has been validated in a related study for this fatty acid¹⁹. It is anticipated to take 10-15mins to complete. Mothers will be asked to complete this questionnaire at the time of enrollment.

Blood samples will be collected 4 times. When possible, and in the majority of blood draws, 1.3 cc of whole blood will be collected at the same time as other blood draws to avoid multiple sticks. Whole blood will be collected in a green or lavender top tube. One hundred μ l of plasma will be isolated, and this will be aliquoted into in two tubes and frozen (-80°C).

Lipidomics: Plasma fatty acids will be tested using a preprandial whole-blood sample (1.3 mL) drawn 2-4 hours after the parenteral nutrition (PN) had ended for the day and after enteral feedings were held for 3 hours if the patient was also fed enterally. The schedule for sampling will be as follows: prior to parenteral nutrition within ≤ 3 days of life; within 5-8 days after parenteral nutrition is started; within 5-8 days after enteral nutrition full feeds is started; and prior to discharge from hospital coinciding with time that ROP may be present. The samples will be sent to [name] of Engineering in Medicine Laboratory at UCSD or another UCSD laboratory for internal validation of assays. [name] lab (UCSD Department of Ophthalmology) or another laboratory with similar capabilities will perform some of the RNA isolation and analysis. Capillary gas chromatography/mass spectroscopy will be the one of the main methods used to determine the phospholipid profile.

Transcriptomics: From the plasma isolated from the whole blood samples, 50 μ l will be used for mRNA isolation. This will be collected and frozen as the study is ongoing. The fold expression of genes associated with the fatty acid synthesis pathway, hypoxia and pro-angiogenic pathways will be correlated with clinical disease.

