The investigational drug pharmacy (IDS) will obtain the Omegaven and dispense it to the nurse for administration in a separate line than the rest of the nutrition (amino acids, sugars, etc). The NICU nutritionist will optimize the total nutritional calories to the infant per NICU protocols. The IDS pharmacist, nutritionist, and NICU team will not be blinded to ensure that the infant in the Omegaven group meets all the nutritional requirements as determined by the NICU neonatology attendings and fellows involved in the study. The ophthalmology team will be blinded to the treatment group to prevent any potential for bias during the eye exam.

Outcome Measures:

Outcome 1: Change in concentrations of basic fatty acids (EPA, DHA, and AA) and their bioactive metabolites will be assessed at multiple time points.

Outcome 2: Change in mRNA expression of TNF- α , PPAR- γ , and VEGF at multiple time points.

Outcome 3: Severity stage of ROP in Group 1 compared to Group 2. This will be assessed at the time of ROP screening (approximately 31 weeks), and the outcome will be measured at approximately 40 weeks adjusted age. The stage of ROP at 40 weeks adjusted will be used for statistical analyses.

Safety:

A data safety monitoring board (DSMB) will be established to monitor the safety of enrolled infants in the study as well as identifying the efficacy of the treatment at ongoing intervals. The DSMB will meet after the first 5 infants are enrolled and then regularly at multiple intervals during the study. Clinical safety assessments will occur during the hospital admission including vital signs, weight, physical exam and laboratory assessments of triglycerides. The neonatologist will review the assessments and determine if the subject should remain in the study or be removed.

Statistical Analysis

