Our primary analytic approach will use generalized linear mixed models (GLMM). These methods will address problems of missing data, variable timing of the subject visits, and other possible unintended violations of design. Although our retention and follow-up plan is designed to minimize missing data, an advantage of the GLM models is that they allow us to maximize statistical power by not excluding subjects with some missing data. More specifically, GLM assumes that the data can be missing at random (MAR) or missing completely at random (MCAR). The benefit of this assumption is with a repeated measure problem (e.g., longitudinal data) you can still analyze data from all subjects, even if some have missing data (assumed MAR or MCAR). Mixed regressions will also allow us to estimate an intercept and slope for each patient based on all available data for that individual augmented by the data from the entire sample, with two random effects being used to model time trends (i.e., a random intercept and a linear trend). Further details of selected analyses related to each outcome are provided next.

For Outcome (a-b), the primary outcome is DHA at a specified period of time (i.e. 40 weeks) to assess the basic fatty acids. Outcome (a) posits that patients in Group 1 will differ from those in Group 2 with respect to i) DHA

ii) EPA iii) AA iv) bioactive metabolites. To assess Outcome (a) (i.e. to evaluate the effects of group, time, and their interaction on the change from baseline DHA measurements), a mixed effects model with group (IV Omegaven then PO baby fish oil or Intralipid), time, and group by time interaction as fixed effects, and random intercept and slope to account for within subject correlation. We expect that the interaction in question will be significant.

For Outcome (c), we hypothesize that Group 1 and Group 2 will have a different severity stage of ROP. To assess Outcome (c), we will use a *Mixed-effects ordinal logistic regression model* with severity stage of ROP after 40 weeks (Stage I, II, III, IV, V) as the outcome variable. The same fixed and random effects mentioned above will be used in evaluating Outcome(c).

All statistical analyses will be performed using SAS software version 9.3 (SAS Institute, Cary, North Carolina, USA).

[figure not shown]
Power Calculations

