16. PRIVACY AND CONFIDENTIALITY CONSIDERATIONS INCLUDING DATA ACCESS AND MANAGEMENT

Absolute confidentiality cannot be promised because information needs to be shared as described below. However, information will be collected and shared following standards of confidentiality. Subjects' identity as a participant in this study will remain strictly confidential. Subjects will be identified in the study under a study-specific code. Should results of this study be published, subjects will not be identified through their name or personal information. All research records will be stored in a locked cabinet at all times. Computers used to store electronic data information, are password-protected and only accessible by study staff.

For the maternal questionnaire, no protected health information will be collected from the mothers that complete this form. We will instead indicate the infant's subject ID on the form to correlate the mother's responses with the data collected on their infant for this study.

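### The maternal omega-3 questionnaire is not required before allocation is known, and the DHA and ROP models leave out birth weight for gestational age (minor)

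*Combined protocol and SAP*

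**What the plan says.** **Timing of the form.** Section 9 (During the study) gives two timings in one paragraph: "Maternal diet questionnaires will be administered to the maternal subjects following enrollment" and "Mothers will be asked to complete this questionnaire at the time of enrollment". The same section places randomisation after enrolment: "If the infant is enrolled in the study, the infant will be randomized in blocks of 4 by gestational age to one of two groups". No interval between the two is stated.

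**Masking.** Section 9 says "The IDS pharmacist, nutritionist, and NICU team will not be blinded" and "The ophthalmology team will be blinded to the treatment group to prevent any potential for bias during the eye exam". Parents are not mentioned as masked, no placebo is described, and Omegaven runs in a separate line.

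**Use of the form.** Section 16 gives the only stated use. The infant's study ID goes on the form in order to correlate the mother's "responses with the data collected on their infant for this study". It names no method and no infant variable, and does not say how arm is handled.

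**Models.** Section 9 (Statistical Analysis) analyses change from baseline DHA with "a mixed effects model with group (IV Omegaven then PO baby fish oil or Intralipid), time, and group by time interaction as fixed effects", plus a random intercept and slope. The ordinal model for ROP stage reuses those terms. Neither model has a term for birth weight, size for gestational age or maternal intake.

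**Background.** Section 7 says "Preterm and small for gestational age infants have altered serum phospholipid fatty acid profiles with lower DHA". It also describes low-birth-weight and premature infants as being at high risk of severe ROP.

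**The concern.** There are two separate matters.

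The first is the order of events. A diet report is a clean baseline measurement only if the respondent does not yet know the allocation. A mother who knows her infant is, or is not, receiving fish oil may recall or report her own omega-3 intake differently. At stake is the value of the questionnaire for the correlation in section 16, and its fitness as a covariate if anyone later wants to use it as one.

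The second is an omitted prognostic variable. Size for gestational age is known for every infant at entry, and the plan's own background ties it to DHA. Blocking by gestational age does not balance it. The entry rule in section 10 also accepts infants under 1500 g as an alternative to the gestational-age range, which on its face admits small infants born after 30 weeks. At stake are some precision and some protection against chance imbalance in a trial planned on 40 completers.

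**Working it through.** **1. Can a mother know the arm when she answers?** The documented order is enrolment, then randomisation. A form completed at enrolment could precede allocation; a form completed after enrolment could follow it. Both timings are permitted and neither is tied to allocation. The documents do not say when parents learn the arm. The only explicit sign that they know it is the weekly call about fish oil to Omegaven-arm parents after discharge (section 9, Nutrition). So the exposure is possible, but not shown for any given mother.

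**2. Where could the effect go?** The fixed effects are group, time and group by time. The score is not among them, so an arm-dependent reporting error cannot enter the estimated treatment effect. It can enter the correlation in section 16.

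**3. The plan's own power figure.** Inputs from section 9 (Power Calculations): 20 per arm, mean changes 42 and 27 µmol/L (difference 15), largest SD 15, two-sided alpha 0.05.

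- Noncentrality = 15 / (15 × √(1/20 + 1/20)) = 3.162, with 38 df.
- Power from the noncentral t distribution = 86.9%. This agrees with the plan's statement of over 80%.
- Smallest difference detectable at 80% power = 13.6 µmol/L.
- At SD 13 power is 94.5%, and at SD 11 it is 98.7%.

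**4. Adding one fully observed baseline covariate.** Residual SD = 15 × √(1 − R²), with 37 df. R² is the share of variance in DHA *change* explained. The documents do not give it, so a range is assumed.

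| Assumed R² | Residual SD | Power | Detectable difference at 80% (µmol/L) |
|---|---|---|---|
| none (plan) | 15.00 | 86.9% | 13.6 |
| 1% | 14.92 | 87.2% | 13.6 |
| 2% | 14.85 | 87.5% | 13.5 |
| 5% | 14.62 | 88.5% | 13.3 |
| 10% | 14.23 | 90.1% | 12.9 |
| 20% | 13.42 | 93.1% | 12.2 |

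Charging 2 df instead of 1 lowers each power by less than 0.1 percentage point. The degree of freedom itself costs almost nothing.

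**5. Chance imbalance.** Assume 15, 25 or 35% of infants are small for gestational age and treat the two arms as independent Binomial(20, p). The probability that the arms differ by 4 or more such infants is then 11.8%, 19.9% or 24.5%.

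**6. Why maternal intake is a weaker candidate for the primary model.** Two checks use an assumed correlation r between the score and DHA change, with r from 0.1 to 0.5.

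- *Missing forms.* Mothers may decline and must be proficient in English (section 10). If 20% of forms are missing and those infants are dropped (16 per arm, 29 df), power is 78.5% at r = 0.1, 81.7% at r = 0.3 and 88.4% at r = 0.5, against 86.9% unadjusted. The loss outweighs the gain unless r exceeds about √0.20 = 0.45.
- *Arm-aware answers.* If knowing the arm shifted reported intake by 0.2 to 0.5 SD in one arm, adjusting for the score would move the treatment estimate by about r × 15 × shift. That runs from 0.1 × 15 × 0.2 = 0.3 to 0.5 × 15 × 0.5 = 3.75 µmol/L, against a planned difference of 15.

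**The case against.** The strongest reply is that little is wrong. The two timings are compatible: the infant is enrolled and the mother is handed a 10 to 15 minute form. An unmasked NICU team does not show that she knows the arm at that moment. Omitting optional covariates is a choice, chance imbalance is already allowed for in the type I error rate, and power is adequate at the plan's worst SD. Most of this stands, and it is why the point is minor. What it does not answer is that no sentence places the form before allocation, and that adjusting for a variable known for every infant is nearly free.

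A reader might infer several stronger things that the documents do not support:

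- *That the treatment effect is biased.* It is not by this route, since the score is outside the models.
- *That the questionnaire is unused.* Section 16 states a use; what is missing is a method.
- *That maternal intake is a known predictor of infant DHA change.* The protocol calls the form validated, but gives no correlation with infant DHA.
- *That the planned correlation pools the arms and is driven by study oil.* Section 16 says neither. A correlation with T0, drawn before parenteral nutrition and preferably from cord blood, would be free of study oil.
- *That small size must explain much of the variance in the outcome.* Section 7 speaks of DHA levels, whereas the analysis is of change from T0, which already absorbs part of any difference in level.

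**Conclusion.** The point holds as two small, separate gaps. The order of questionnaire and allocation is left open, which puts the questionnaire data and the maternal-infant correlation at risk but not the treatment estimate. The DHA and ROP models omit birth weight for gestational age, which the background gives reason to include and the randomisation does not balance.

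The benefit for DHA at SD 15 is about 1.6 to 6.2 percentage points of power if R² is 5 to 20%, under 1 point if R² is 1 to 2%, and smaller at the plan's lower SDs. All of this rests on an assumed R² for change, a two-sample approximation to the mixed model, and 40 completers. The imbalance figures rest on assumed prevalence. No gain is quantified for ROP, where the plan gives no power calculation. Severity is minor.

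**What to change.** 1. **Section 9 (During the study):** replace the two timings with one, so that the form is completed after consent and before allocation is revealed. Record the date and time of completion.
2. **Section 9 (Statistical Analysis):** prespecify birth-weight z-score for gestational age (or small-for-gestational-age status) as a fixed covariate in the DHA and ROP models.
3. **Maternal-infant correlation:** state that it will be reported with T0 DHA and, if at later times, within arm or adjusted for arm.
4. **Maternal intake:** use it as a covariate only in a prespecified sensitivity analysis, with a stated rule for missing forms and only if item 1 is in place.

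The cost is one degree of freedom in each model and a few sentences of text. No new clinical data are needed. Item 1 asks for the form in the early period around consent, and it cannot be repaired afterwards for mothers who have already answered knowing the arm; for them, the recorded time of completion would at least allow the affected forms to be identified.

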Fatty acid supplementation will continue until the baby is full term (40 adjusted weeks of age). If the infant is discharged before he/she is full-term, the infant will be sent home with a bottle of the fatty acid oral solution for the infant to continue daily until he/she is full-term (40 weeks of age). The infant's nutritional needs will be carefully monitored by his/her doctor and nutritionist per NICU protocols.

To monitor the amount of fatty acid nutrition getting into the blood, we will check the infant's blood. As much as possible, we will coordinate the study blood collection at the same time as the routine NICU blood draws. We will collect 1.3 milliliters of blood at 4 different times spread apart while the infant is in the hospital. At each time point, we will collect about 1/4 teaspoon of blood, for a total of about 1 teaspoonful.

The blood draws will occur as the following four time points:

- Blood draw T0= Prior to parenteral nutrition, within 1st 3 days of life. This blood collection should be

taken from cord blood. If cord blood is not available, sample will be collected from a UAC, UVC, or peripheral blood draw concurrent with SOC.

- Blood draw T1= 5 days after parenteral nutrition is started; grace period +/-3 days therefore total 2-8 days after parenteral nutrition started.
- Blood draw T2= 5 days after enteral nutrition full feeds have arrived; grace period +/-3 days therefore total 2-8 days after full enteral nutrition arrived.
- Blood draw T3= Prior to discharge from hospital coinciding with time that ROP may be present, ≥ 35 weeks adjusted age.

This blood will be used for looking at what new genes (mRNA) the infant is making and to check how many and what kind of fatty acids the infant has in the blood. Before testing, the blood will be stored in a storage facility at the UCSD Department of Ophthalmology Blood Bank and labelled with a barcode without the infants' personal information. This is not the infant's DNA, and no DNA will be isolated or tested. Samples will be stored for 10 years. After this time point, all samples will be destroyed if not used by that time. If the parent decides to withdraw consent the blood samples that were already drawn will be destroyed, however, any previously obtained data from sample testing will be kept.

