Infants in the experimental group will be getting Omegaven® for parenteral nutrition in addition to the standard nutritional requirements (Intralipid within a 3:1 TPN). Omegaven dose will be dosed per weight to give goal dose of 1 g/kg/day infused over 12 to 24 hours with the intention to run over 24 hours. Initial Omegaven dose will be between 0.5 g and 1 g/kg/day. If the infant’s nutritional lipid requirements are for more than 1g/kg/day, the remaining calories from fat in the experimental group will be derived from Intralipid (the parenteral lipid emulsion used most often in the UCSD’s NICU). Additional triglyceride testing should not be necessary given dosing²⁰.

Infants in the control group will be getting the standard of care, which is Intralipid® combined with the standard nutritional requirements in a 3:1 TPN. Intralipid will be used according to the Dosage and Administration information in the package insert up to 3.5 g/kilo/day. Initial dose is between 0.5 g and 1 g /kg, starting at 18:00 and running for 24 hours. Total daily dose will be infused over 12 or 24 hours based on provider preference.

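### The T1 fatty-acid sample is timed from a daily end of parenteral nutrition that infants on the intended 24-hour infusion do not have, so time since infusion will vary and may differ by arm

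*Combined protocol and SAP*

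**What the plan says.** All the relevant text is in Section 9 of the combined protocol and SAP.

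- **Sampling rule (Lipidomics).** The plasma sample is to be "drawn 2-4 hours after the parenteral nutrition (PN) had ended for the day". An infant who is on enteral feeds as well must also have gone 3 hours without them.
- **Experimental arm (Nutrition).** Omegaven is "infused over 12 to 24 hours with the intention to run over 24 hours". These infants also receive Intralipid within their TPN, and Omegaven goes through its own line.
- **Control arm (Nutrition).** The initial Intralipid dose is described as "starting at 18:00 and running for 24 hours". The next sentence reads "Total daily dose will be infused over 12 or 24 hours based on provider preference".
- **Draw schedule.** T0 precedes parenteral nutrition (PN). T1 follows the start of PN, with a "grace period +/-3 days therefore total 2-8 days after parenteral nutrition started". T2 follows full enteral feeds, and T3 is taken before discharge at 35 weeks adjusted age or later.
- **Logistics.** "As much as possible, we will coordinate the study blood collection at the same time as the routine NICU blood draws".
- **Analysis (Statistical Analysis).** The named primary outcome is DHA at 40 weeks. The model is for change from baseline, with group, time and their interaction as fixed effects and a random intercept and linear slope. The interaction is expected to be significant.

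Nothing in the section says how to sample an infant on continuous PN, or asks for infusion status or time since infusion to be recorded at the draw.

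**The concern.** The Lipidomics rule presumes PN that stops each day. The Nutrition paragraphs make a 24-hour run the intention for Omegaven and the description of the initial control infusion. Under that schedule there is no stop to count from.

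Staff will have to improvise. Some T1 samples will be taken with lipid running and others 2-4 hours after it stopped, and the data will not show which is which. If plasma DHA depends on whether emulsion is running, this adds variation between infants at T1. If the mix differs between arms, it also adds a timing component to the arm difference at T1. The second possibility cannot be dismissed: Omegaven has a stated 24-hour intention, control duration is left to the provider, and the NICU team knows the allocation.

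T1 is the trial's only routine measurement of the parenteral phase, and infusion status that is not recorded at the draw may not be recoverable later.

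**Working it through.** **1. The plan's own figure.** Inputs from Power Calculations: 20 per arm, difference 42 − 27 = 15 µmol/L, SD 15, two-sided 0.05. The two-sample t-test has power 86.9% (exact noncentral t) or 88.5% (normal approximation). Both agree with the stated figure of over 80%. The figure caption places this comparison at 40 weeks, so the T1 conflict does not change it.

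**2. Is there a sampling window?** Let D be the hours per day that any PN is running, assuming the same run is repeated daily.

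- Hours off PN = 24 − D
- Usable part of the 2-4 hour window = max(0, min(4, 24 − D) − 2)

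| D (hours) | Hours off PN | Usable window (hours) |
|---|---|---|
| 12 | 12 | 2 |
| 18 | 6 | 2 |
| 20 | 4 | 2 |
| 21 | 3 | 1 |
| 22 | 2 | 0 |
| 24 | 0 | 0 |

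The rule can be met in full up to 20 hours and not at all from 22 hours. In the experimental arm D covers Omegaven and the TPN together, so a pause in one line alone does not end PN.

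**3. Which draws are affected?** T0 comes before PN. Omegaven stops at the enteral transition, and T2 and T3 follow full feeds. Only T1 is normally drawn on PN.

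**4. Does timing differ by arm?** Let p be the share of an arm's T1 samples drawn with lipid running, and s the mean DHA shift from drawing then instead of 2-4 hours after the stop. The timing component of the arm difference is

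p(E)·s(E) − p(C)·s(C)

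where E is experimental and C control. If s is the same in both arms, this is (p(E) − p(C))·s. It is zero when the mix is the same and at most s, in either direction, when one arm is sampled entirely on lipid and the other entirely off. The documents give neither p nor s. Because the emulsions differ, s(E) = s(C) is itself not assured.

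**5. What does a T1 shift do to the trend?** In an ordinary least-squares line, a shift δ at T1 changes the slope by δ(t1 − t̄)/Σ(t − t̄)². Take an infant born at 30 weeks, so that T3 is at least 35 − 30 = 5 weeks, or 35 days, after birth. Assume PN starts by day 3, so T1 is no later than day 3 + 8 = 11, and assume T2 is no earlier than T1. Even with T1 and T2 both at day 11, t̄ is at least (0 + 11 + 11 + 35)/4 = 14.25 days, or (11 + 11 + 35)/3 = 19 days without T0. Hence t1 < t̄: a raised T1 value lowers the fitted slope.

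**The case against.** The best case for the plan is that shorter infusions are permitted in both arms, so the rule is feasible for some infants, and that both arms can also run 24 hours, so the timing mix could be identical. The routine-draw sentence is a preference, not a competing timing rule. T1 is not the named primary time point. The section also says that the draws monitor how much fatty acid reaches the blood, so circulating infused DHA is arguably part of what T1 should capture.

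Most of this stands, and it limits the point. Four stronger inferences are tempting, and the documents do not support them:

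- **That the rule can never be followed.** It fails only at about 22 hours or more.
- **That timing will differ by arm and favour Omegaven.** A difference is possible but not shown. For the slope and interaction, a raised T1 in the Omegaven arm would pull the other way (step 5).
- **That the primary comparison is biased.** DHA at 40 weeks is not measured on PN. T1 could reach it only indirectly, if the 40-week value were read from the fitted line.
- **That the type I error is inflated by a calculable amount.** The plan specifies no separate T1 test, and the documents give no shift to put into one.

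The objection does not remove the contradiction itself. The rule fails under the schedule that the plan intends for the experimental arm. If infused DHA is the target at T1, a post-infusion sample is the wrong definition of it. Either way the text needs a decision.

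**Conclusion.** The point holds in limited form. At T1 the sampling rule cannot be met by infants on PN for about 22 hours a day or longer, which includes the intended 24-hour Omegaven run and the 24-hour run given for the initial control Intralipid. Time since infusion will vary between infants and may differ by arm.

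The certain part is the lost window: 0 of 2 hours at 24 hours of infusion, against the full 2 hours at 12 to 20. The effect on measured DHA is unknown in size and direction. The reach is the T1 contrast, the fitted time trend and the group-by-time interaction. The stated power at 40 weeks is untouched.

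This rests on daily runs of constant length and on T2 and T3 being drawn off PN, as the draw schedule implies. It is worth correcting before samples are collected, but it is not a threat to the trial's main comparison.

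**What to change.** 1. **Reconcile the Lipidomics and Nutrition text**, leaving the infusion schedule as it is. Settle the T1 day window at the same time: the draw list gives 2-8 days after the start of PN, the Lipidomics paragraph 5-8.
2. **Write one T1 draw rule, the same in both arms, that can be met under every permitted infusion length.** One option is a set interval within the first 12 hours after the daily lipid start. The shortest permitted run is 12 hours in both arms, so lipid would then be running for every infant who follows the schedule. This gives up the post-infusion sample, and hourly rates would still differ between 12- and 24-hour runs. Say how the rule combines with the feed-hold condition, and that routine draws are used where they fit it.
3. **Record at each draw** the draw time, whether PN or lipid was running and, if not, the hours since it stopped.
4. **Pre-specify two sensitivity analyses of DHA**: one adjusting for or stratified by infusion status at the draw, and one leaving out T1. Infusion status arises after randomisation and may be tied to arm, so the first is supportive only. Without T1 just two post-baseline draws remain, so state in advance whether the random slope will be dropped. Do not simply omit every sample drawn during infusion: if the 24-hour intention is followed, that discards most Omegaven T1 samples.

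The cost is protocol wording, a few fields on the sample form and a small amount of extra analysis.
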